10.3. CONFIDENTIALITY

All information obtained during the conduct of the study will be regarded as confidential. An agreement for disclosure will be obtained in writing by the patient and will be included in the ICF. Patient's data collected during (or after completion of) the study will be handled in accordance with applicable data protection laws and regulations.

On the CRFs or Diary Cards, patients will be identified ONLY by the assigned patient number. If patient names are included on copies of documents submitted to Dompé or the CRO appointed by Dompé, the names will be obliterated or masked and the assigned patient number added to the document.

The Investigator should keep a separate log (Patient Master List) of patient's codes, names and addresses.

10.4. COMPENSATION FOR MEDICINE-INDUCED INJURY AND INDEMNIFICATION

Before the trial formally starts, Dompé will take out a study-specific insurance covering the amount requested by the respective national laws for patients/Investigators/Institutions participating in the clinical trial.

In case of questions about medical care, cost for medical care or insurance, patients can talk to their Investigator. Contact details will be given in the ICF.

Insurance and any updates will be provided to the Investigator before trial commencement for filing into the Investigator Site File.

11. DATA HANDLING AND RECORD KEEPING

11.1. CASE REPORT FORMS

CRFs will be supplied as 3-pages/ No-Carbon Required binder. CRFs are the sole property of Dompé and should not be made available in any form to third parties, except for authorized Dompé' designee or representatives of appropriate Health/Regulatory Authorities, without written permission from Dompé.

A CRF is required and should be completed for each patient enrolled. The Investigator will be responsible for the accuracy of the data entered in the CRFs. All entries must be written in ***ENGLISH*** in black ink. Source documents should be available to support all the data recorded in the CRF; location of source documents, including those for which the CRF might be accepted as being the sole source document, will be specified and listed at the centre Initiation Visit.

The CRF must be available for review/collection to designated Dompé's representatives at each scheduled monitoring/audit visit.

11.2. DIARY CARD

Diary Cards will be supplied as a single-page document. They are the sole property of Dompé and should not be made available in any form to third parties, except for authorized Dompé' designee or representatives of appropriate Health/Regulatory Authorities, without written permission from Dompé.

A Diary Card (local language version) will be provided to each patient randomized into the trial. A sample English specimen is provided in **Appendix 14.2**.

The patient will report in the Diary Card the details (date, time, number of capsules) of each administration of the IMP. It is responsibility of the Investigator to explain to each patient how to enter the data in the Diary Card and to check the Diary Card returned to ensure correct completion as well as correct intake of the IMP.

11.3. DATA MANAGEMENT

Data management of the CRFs and Diary Cards will be performed by the CRO appointed by Dompé.

The CRF and Diary Card pages for all patients will be data-entered (double data entry) into the study data-base, and the data will be verified for missing data, inconsistencies, and for any necessary medical clarifications. Queries arising from these checks will be sent to the Investigator for response and signature.

Once all data queries have been resolved, the study data-base will be declared to be "clean", and the study data will be locked ready for analysis.

After the database lock has been achieved, the Investigator may archive the copies of the CRFs and Diary Card retained at the centre. The original CRF and Diary Card will be transferred to Dompé for archiving.

11.4. DOCUMENTATION REQUIRED PRIOR TO INITIATION OF AND DURING THE STUDY

In addition to the documents mentioned in **Sections 10.1** and **12.1**, the following documents will be required from the Investigator prior to the initiation visit (and during the course of the study in case of any update):

- Current, signed and dated Curriculum Vitae of Principal Investigator and any Sub-Investigators/co-workers. Updates should be provided at least every two years.

- Normal ranges of all laboratory tests to be performed at the study site and a recent certification or accreditation of established quality control (or other documentation of established quality control or external quality assessment or other validation). Updates should be provided as soon as any reference value has changed.
- A signed page of the final protocol and any amendments.
- A signed copy of the study Financial Agreement/Clinical Study Agreement with Dompé (or designee), including all study specific costs.
- List and any updates of delegated responsibility (Study Team Signature List / Delegation of Responsibilities form).

11.5. ESSENTIAL DOCUMENT RETENTION

The Investigator will retain copies of all the essential documents (as defined by ICH-GCP) until at least 2 years after the last approval of a marketing application in an ICH region, and until there are no pending or contemplated marketing applications in an ICH region, or at least 2 years have elapsed since the formal discontinuation of clinical development of the Investigational Product. These documents should be retained for a longer period however if required by the applicable regulatory requirements. The Investigator should take measures to prevent accidental or premature destruction of these documents.

The essential documents include, but are not limited to: the signed protocol, copies of the completed CRFs, and Diary Cards, signed Patient Informed Consent Forms from all patients who consented, hospital records and other source documents, and all other documentation included in the Investigator Site File and Pharmacy/Dispensing File.

The Investigator will inform Dompé (or designee) of the storage location of these essential documents and must contact Dompé before disposing of any. If the Investigator wishes to assign the files to someone else or to remove them to another location, he/she should consult with Dompé about this change.

Dompé will inform the Investigator in writing when these documents no longer need to be retained.

12. STUDY MANAGEMENT

The study will be performed in accordance with the protocol, the Declaration of Helsinki (64th WMA General Assembly, Fortaleza, October 2013) and ICH Harmonised Tripartite Guideline for Good Clinical Practice (*ICH-GCP*) and any local regulations.

12.1. REGULATORY BODY APPROVAL

The CRO appointed by Dompé will obtain the necessary approval from the Competent Authorities prior to initiation of the study.

The study will not be started until full written approval from the relevant Competent Authorities has been received by Dompé.

12.2. STAFF INFORMATION & RESPONSIBILITIES

It is the responsibility of the Investigator to ensure that all personnel involved in the study are fully informed of all relevant aspects of the study, including detailed knowledge of and training in all procedures to be followed.

The Investigator will maintain a list of delegated responsibility detailing the various study tasks to be performed by each member of his/her study staff. Each staff member should sign in agreement to their performing each of the tasks delegated to them on the list.

12.3. MONITORING

Monitoring will be carried out by CRAs of CRO appointed by Dompé.

The purpose of the monitoring visit is to verify that the rights and the wellbeing of the patient are protected, that the reported data are accurate, complete and verifiable from source documents and that the conduct of the trial complies with the currently approved protocol and any amendments, with ICH GCP, and with regulatory requirements.

Prior to study start, the Investigator will be informed of the anticipated frequency of the monitoring visits. (S)He will also receive a notification prior to each monitoring visit during the course of the study. It is expected that the Investigator and/or his/her sub-Investigator(s) and other appropriate staff will be available on the day of the visit to discuss study conduct and to cooperate with the monitor to ensure that any problems detected during the course of these monitoring visits are resolved.

12.3.1. Access to records

The Investigator will allow designated Dompé representatives, including staff from the appointed CRO, and regulatory/ethics bodies to have direct access to the source documents to verify the data reported in the CRFs. Source documents are the originals of any documents used by the Investigator or hospital/institution that allow verification of the existence of the patient and substantiate the integrity of the data collected during the trial.

12.4. AUDIT AND INSPECTION

Audit activities will be performed by the Dompé Quality Assurance Unit or any other third party delegated by Dompé or by the CRO, as appropriate.

12.5. PROTOCOL DEVIATIONS/AMENDMENTS

Changes to the Protocol will be implemented only when written amendments have been signed by all individuals who signed the protocol.

Any amendment will be sent to the IEC and Competent Authority as appropriate. No deviations from or changes to the protocol will be implemented without documented approval of an amendment from the IEC which granted the original approval, except where necessary to eliminate an immediate hazard(s) to trial patient, or when the change(s) involves only logistical or administrative aspects of the trial. The deviations from or changes to the protocol implemented to eliminate an immediate hazard to the trial patient and the proposed amendment, if appropriate, should be submitted to the IEC for review and approval as soon as possible.

Any other deviation from the protocol that has not been approved by Dompé and the IEC could result in a discontinuation from the study at the centre involved.

Any written amendment will be sent to all recipients of the protocol.

12.6. DISCONTINUATION OF THE STUDY

Dompé reserves the right to stop the study at any time on the basis of new information regarding safety or efficacy, or if study progress is unsatisfactory, or for other valid administrative reasons.

After such a decision is made, the Investigator must inform all relevant persons e.g. study staff, potential patients etc. within 2 weeks. All delivered study materials must be collected and all CRFs/Diary Cards completed to the extent possible.

Study discontinuation will be notified to Competent Authorities within 15 days from decision.

12.7. PUBLICATIONS

As this study is part of a multicentre trial, publications derived from this study will be planned and agreed with the participating Investigators. Publications will include input from the Investigators, his/her colleagues, other investigators in this trial and Dompé personnel. Such input will be reflected in publication authorship. Criteria for selection of authors will be agreed. Subsequent to the multicentre publication or one year after completion of the study, whichever occurs first, an Investigator and/or his/her colleagues may publish the results of Investigator's part of the study independently.

Any manuscript, abstract or other publication or presentation of results or information arising in connection with the study must be prepared in conjunction with Dompé and must be submitted to the Dompé for review and comment at least 45 days prior to submission for publication or presentation. If such draft contains confidential patentable information, the Investigator will refrain from publishing any such information for a period not exceeding 180 days, to enable Dompé to file for the protection of any intellectual or proprietary property interest.

14. APPENDICES

14.1. APPENDIX 14.1 - PACKAGING AND LABELING DETAILS

A Patient Kit will be prepared for each patient, containing 3 Treatment Boxes, one for each treatment cycles. Each Treatment Box will contain 7 blisters of 8 pockets each, for a total of 56 capsules (amount needed for each treatment cycle).

All items will have local language labels. The template of the English label is provided below. Label content will be adjusted to meet local regulatory requirements. Only the label of the “Treatment Box” will be a “double - tear off” label.

NOTE: Patient No. XXYY where XX = Study site; YY = Patient sequential number at the site
Treatment cycle No. Z where “Z” can be either 1, or 2, or 3

Specimen Label for each Patient Kit

STUDY MEX0114	Sponsor Dompé farmaceutici s.p.a.; [name]	
	INVESTIGATOR: (name)	
PATIENT No. XXYY		
INVESTIGATIONAL PRODUCT: ladarixin (200 mg) or placebo oral capsules		
CONTAINS: 3 TREATMENT BOXES, ONCE FOR EACH TREATMENT CYCLE; TOTAL 168 CAPSULES (IN 21 BLISTERS)		
coded BATCH No.	coded EXPIRY DATE mm/yyyy	DO NOT STORE AT >30°C DO NOT FREEZE
DIRECTIONS: Dispense the Treatment Box, corresponding to the cycle, just before the planned start of that treatment cycle. For any questions, please contact (to be identified in the final label) For clinical trial use only. Box not to be dispensed to the patient.		

Specimen Label for each Treatment Box [double - tear off label]

STUDY MEX0114	Sponsor Dompé farmaceutici s.p.a.; [name]	
	INVESTIGATOR: (name)	
PATIENT No. XXYY	TREATMENT BOX – CYCLE No. Z	
INVESTIGATIONAL PRODUCT: ladarixin (200 mg) or placebo oral capsules		
CONTAINS: 7 BLISTER WITH 8 POCKETS EACH; TOTAL 56 CAPSULES		
coded BATCH No.	coded EXPIRY DATE mm/yyyy	DO NOT STORE AT >30°C DO NOT FREEZE
DIRECTIONS: Take the drug twice a day (2 capsules in the morning and 2 in the evening) for 14 consecutive days. See additional instructions in the Diary Card . Contact the Investigator (see Diary Card) should you have any questions. For clinical trial use only. Keep out of reach of children.		

Specimen Label for each blister

STUDY MEX0114	Sponsor Dompé farmaceutici s.p.a.
	INVESTIGATOR: (name)
coded BATCH No.	coded EXPIRY DATE mm/yyyy
PATIENT No. XXYY	Cycle No.
For clinical trial use only. Keep out of reach of children.	

14.2. APPENDIX 14.2 – SAMPLE DIARY CARD [English specimen]

Clinical Trial MEX0114 - Sponsor: Dompé farmaceutici s.p.a.						DIARY CARD				
PATIENT No.    		TREATMENT CYCLE No. 		INVESTIGATOR NAME and CONTACT DETAILS: _____						

The study doctor has provided you with a Treatment Box containing the study drug for the treatment cycle reported above. Each day, you are requested to take 2 capsules in the morning and 2 capsules in the evening. Please swallow the 2 capsules with a glass of water, 2 hours apart from breakfast or dinner, ideally in the period 8.30/9.30 and 20.30/21.30, respectively. Any time you take the study drug, please report below the number of capsules taken, and the date and time when you take the capsules. Please enter the information with indelible ink. Please, DO NOT DISCARD any of the blisters provided. All the blisters, either unused or empty MUST remain in the Treatment Box. Return the Treatment Box to the study doctor during the next study visit, together with this Diary Card.
										
Day	Date day/month/year		Time 24 hour clock, e.g. 18.30	No. of capsules		Day	Date day/month/year		Time 24 hour clock, e.g. 18.30	No. of capsules
Day 1		Morning				Day 8		Morning		
		Evening						Evening		
Day 2		Morning				Day 9		Morning		
		Evening						Evening		
Day 3		Morning				Day 10		Morning		
		Evening						Evening		
Day 4		Morning				Day 11		Morning		
		Evening						Evening		
Day 5		Morning				Day 12		Morning		
		Evening						Evening		
Day 6		Morning				Day 13		Morning		
		Evening						Evening		
Day 7		Morning				Day 14		Morning		
		Evening						Evening		

Investigator's signature (for review): _____

date: _____

14.3. APPENDIX 14.3 – STUDY FLOW CHART

		100 days														
		VISIT	SCREENING (one or more visits)		Pre-dose visit (2nd cycle)	Pre-dose visit (3rd cycle)	FU visit 3months	FU visit 6months	FU visit 12months							
		Week	From enrolment	- 3 to 0	1-2	4	5-6	8	9-10	11 12	13±1	24 25	26±2	50 51	52±2	
1st INSULIN ADMINISTRATION	ENROLLMENT (consent signed)	ASSESSMENTS	Past medical history and disease-specific information	BP/HR, Weight, Height Safety lab test (hematology & biochemistry) 12 lead ECG Pregnancy	RANDOMIZATION – STUDY DAY 0 [1 st cycle IMP dispensed]	Treatment cycle No.1 (start on Study Day 1)	BP/HR Safety lab test (hematology & biochemistry) 12 lead ECG (repeat 1 hour apart if QTcF is EITHER > 500 msec OR has increased by > 60 msec from screening value) Pregnancy	Treatment cycle No. 2	serum creatinine and albumin, total bilirubin, ALT/AST, 12 lead ECG (repeat 1 hour apart if QTcF is EITHER > 500 msec OR has increased by > 60 msec from screening value) Pregnancy	Treatment cycle No. 3	Pre-visit phone call	Insulin (IU/kg/day) Severe hypoglycaemia HbA1c, Auto-Ab and miR-375	Pre-visit phone call	Insulin (IU/kg/day) Severe hypoglycaemia HbA1c, Auto-Ab and miR-375	Pre-visit phone call	Insulin (IU/kg/day) Severe hypoglycaemia HbA1c, Auto-Ab and miR-375
			Auto-Ab to confirm diagnosis	Baseline Insulin (IU/kg/day) Baseline \$ HbA1c, Auto-Ab and miR-375			MMTT C-peptide glucose glucagon		MMTT C-peptide glucose glucagon			MMTT C-peptide glucose glucagon				
				Baseline MMTT# C-peptide, glucose, glucagon			2 nd cycle IMP dispensed if no contraindication has arisen (see discontinuation criteria below*)		3 rd cycle IMP dispensed if no contraindication has arisen (see discontinuation criteria below*)			BP/HR Safety lab test (hematology & biochemistry)				
			T-cell response ex vivo §								T-cell response ex vivo §		T-cell response ex vivo §		T-cell response ex vivo §	

Assay of green entries will be done at a centralized laboratory. Auto-Antibodies (Auto-Ab) include anti-GAD; IAA; IA-2 antibody; ZnT8. [\$ Baseline Auto-Ab test will not be repeated if test to confirm diagnosis is done within the -3 to 0 week timeframe].

= Baseline MMTT should be planned to ensure the sample is sent to the centralized laboratory and C-peptide result is available (consider 5 working days) in time for randomization.

§ = T-cell to be collected at selected sites only.

* = As per Treatment discontinuation criteria, **no IMP will be dispensed** in the case: QTcF is either > 500 msec or increases by > 60 msec from screening measurement on two consecutive ECG readings taken 1 hour apart; Patient develops LBBB, or atrio-ventricular or heart block; or any significant cardiovascular disease; Patient develops renal (calculated CLcr < 60 mL/min) or hepatic (increased ALT/AST > 3 x ULN and increased total bilirubin > 3mg/dL [>51.3 µmol/L]) dysfunction as well as hypoalbuminemia; Female patient has become pregnant.

Randomization = Study Day 0 with reference to **Study Day 1 = first day when the IMP administration is started.**

14.4. APPENDIX 14.4 - METHODOLOGICAL DETAILS

14.4.1. Handling of samples for centralized assay

A study-specific Laboratory Manual will be issued to all sites, reporting detailed instructions for blood sampling, and preparation, storage and shipment of samples.

The protocol requires that either cell-free serum (blood allowed to clot and centrifuged) or EDTA whole blood samples are stored between -70°C and -80°C until shipment to the centralized laboratory. A refrigerated centrifuge will also be required.

Samples will be shipped from the site to the centralized laboratory in appropriate package in dry ice (solid CO₂) to maintain frozen conditions. All samples will be shipped on an ongoing basis during the trial, according to logistics. However, samples from the last patient visits will be shipped as soon as possible to ensure timely availability of results.

Handling of samples on receipt at the centralized laboratory and assay methods will be described in detail in the Laboratory Manual. Similarly, arrangements will be made for back-communication of the results to the sending site. Once received from the centralized laboratory, each site will enter values pertaining to its patients in the corresponding CRF.

All samples will be destroyed after final study report has been issued or after the patient has withdrawn his/her consent.

Tubes and labels for blood withdrawal and sample storage will be provided by the CRO appointed by Dompé, along with storage and shipment tracking forms. The appointed CRO will also coordinate shipment to the centralized laboratory.

All steps will be tracked to ensure correct data reporting.

Any laboratory involved in centralized assay will be listed in the Laboratory Manual, along with relevant contact details.

14.4.2. Mixed Meal Tolerance Test

The MMTT will be performed after an overnight fast, according to [Greenbaum \(2008\)](#) at baseline (within 1 week prior of randomization) and at each follow-up visit on weeks 13_±1, 26_±2 and 52_±2. Screening MMTT should not be performed within one week of resolution of a diabetic ketoacidosis event, defined as the presence of hyperglycemia (blood glucose >200 mg/dL); pH <7.3 or HCO₃ <15; ketones positive in the serum or urine.

Prior to the test, patients will withhold long-acting insulin on the morning of the test. Rapid-acting and short-acting insulin will be allowed up to 6hrs and 2 hrs, respectively, before the test. Test will be re-scheduled if the patient has a capillary glucose value of >200mg/dL or <70mg/dL.

The test will be initiated before 10 a.m. After 2 pre-meal basal samples have been drawn between -20 to 0 min (basal 1 and basal 2), patients will be given 6mL/kg of Boost[®] High Protein Nutritional Drink (Nestlé Nutrition) up to a maximum of 360mL, to be drunk within 5 min. Post-meal samples will be drawn at 15_±5, 30_±5, 60_±10, 90_±10, 120_±15, 180_±15 min after the meal.

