5.1. INCLUSION CRITERIA

To be eligible for inclusion into this study, each patient must fulfil the following inclusion criteria.

1. Male and female patients aged 18-45 years, inclusive;
2. New-onset T1D (randomization within 100 days from 1st insulin administration);
3. Positive for at least one diabetes-related auto-antibody (anti-GAD; IAA, if obtained within 10 days of the onset of insulin therapy; IA-2 antibody; ZnT8);
4. Require, or has required at some time, insulin, with the exclusion of patients taking twice daily pre-mixed insulin or on insulin pump;
5. Residual β -cell function as per peak stimulated (MMTT) C-peptide level $>0.6\text{ng/mL}$ (0.2nmol/L); MMTT should not be performed within one week of resolution of a diabetic ketoacidosis event;
6. Patient able to comply with all protocol procedures for the duration of the study, including scheduled follow-up visits and examinations;
7. Patients who have given written informed consent prior of any study-related procedure not part of standard medical care;

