6.5.2. Restriction on allowed prior and concomitant medications

The following medications **should not be used** prior to enrolment and up to the end of study participation:

Drugs that affect glucose homeostasis or its readout

- Twice daily pre-mixed insulin or insulin pump;
- Metformin, sulfonylureas, glinides, thiazolidinediones, exenatide, liraglutide, DPP-IV inhibitors or amylin, or any medications known to influence glucose tolerance (e.g. β -blockers, angiotensin-converting enzyme inhibitors, interferons, quinidine antimalarial drugs, lithium, niacin, etc) [off period before randomization = 2 weeks];
- Any immunosuppressive medications, including oral, inhaled or systemically injected steroid, and any other investigational agents, including any agents that impact the immune response or the cytokine system [off period before randomization = 1 month].

Drugs metabolized by CYP2C9 with a narrow therapeutic index (drugs that may have their plasma concentration and effect altered by inhibition of CYP2C9 by ladarixin).

- Phenytoin, warfarin, sulphanylurea hypoglycemics (e.g. tolbutamide, glipizide, glibenclamide/glyburide, glimepiride, nateglinide) and high doses of amitriptyline (> 50 mg/day).

The following medications **can be used with the restrictions detailed below**:

- Non-steroidal antiinflammatory drugs (e.g. ibuprofen, flurbiprofen, indomethacin, piroxicam, naproxen, meloxicam, lornoxicam, celecoxib) can be used during treatment with ladarixin up to a maximum of 3 consecutive days, with a 3 days washout before re-treatment, if any (excluded patients with known hypersensitivity to non-steroidal antiinflammatory drugs).
- Administration of low doses amitriptyline (< 50 mg/day) is allowed under clinical monitoring for possible side effect (e.g. sedation and anticholinergic symptoms). In case a concern is raised, treatment with either amitriptyline or ladarixin should be immediately discontinued.
- Any drug that is known to be a substrate for cytochrome CYP2C9 should be considered for possible drug-drug interaction as per warnings/precautions reported in the Summary of Product Characteristics. Any possible concern should be discussed with the sponsor Medical Expert prior to patient enrolment or concomitant administration with ladarixin.

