7.1. ENROLMENT, SCREENING AND RANDOMIZATION

7.1.1. Enrolment and Intensive Diabetes Management

Potential study patients with a recent clinical diagnosis of T1D will be identified from those referring to the site for diagnosis confirmation (auto-antibody testing) and/or disease management.

Enrolment is defined as signature of the Informed Consent Form (ICF) for study participation.

From enrolment, patients will be admitted to an intensive diabetes management, according to current ADA recommendation [2014]. Patients will be instructed to self-monitor their glucose values at least 4 times a day and to report (glucose meter/log) outcome to the diabetes management team. Insulin intake will be adjusted to target HbA1c levels of less than 7% and self-monitored (fingerstick):

- pre-prandial blood glucose of 70-130 mg/dL
- post-prandial blood glucose < 180 mg/dL
- bed-time blood glucose of 110-150 mg/dL

Telephone calls (outside scheduled visits) will be scheduled on a regular basis to ensure optimization of metabolic control. It is expected that patients are contacted at least every 2 to 3 weeks during study participation. A telephone call will be anyway scheduled in the 2 weeks before a planned visits (as detailed in the sections below) to enable the Investigator to review glucose data and confirm/adjust insulin intake to be applied for at least 3 days before the visit.

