### 6.5. PROTOCOL DEVIATIONS

All the protocol deviations will be discussed case by case by the clinical team during the review of the data before the lock of the study database and described in the Blind Data Review Report.

However, the following protocol deviations are anticipated to be considered as major:

- Inclusion and exclusion criteria not respected;
- Received treatment other than they were randomized to;
- Missing information on IMP administration that does not allow calculation of IMP exposure/compliance;
- Overall study treatment compliance < 80%;
- Incorrect Boost dose at one or more MMTT visits;
- Missing data for the primary endpoint (AUC C-peptide from MMTT at week 13);
- Primary endpoint (AUC C-peptide from MMTT) at week 13 assessed out-of-window visit ( $\pm 1$  week);
- Use of prohibited concomitant medications prior to enrolment and up to the end of the study participation (Concomitant treatment with phenytoin, warfarin, sulphonylurea hypoglycemics (e.g. tolbutamide, glipizide, glibenclamide/glyburide, glimepiride, nateglinide) and high dose of amitriptyline (> 50 mg/day), concomitant treatment with metformin, sulfonylureas, glinides, thiazolidinediones, exenatide, liraglutide, DPP-IV inhibitors or amylin, or any medications known to influence glucose tolerance (e.g.  $\beta$ -blockers, angiotensin-converting enzyme inhibitors, interferons, quinidine antimalarial drugs, lithium, niacin, etc.), current administration of any immunosuppressive medications (including oral, inhaled or systemically injected steroids) and use of any investigational agents, including any agents that impact the immune response or the cytokine system);
- Concurrent illnesses/TEAEs that may impact the glycemic control or trial read-out, to be defined case by case.

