## 16.2. SECONDARY EFFICACY ANALYSES

### 16.2.1. SECONDARY EFFICACY VARIABLES

The secondary efficacy variables are:

1. 2-hour AUC of C-peptide response to the MMTT [Time points: baseline, weeks 13±1, 26±2 and 52±2].
2. Percent change from baseline of 2-hour AUC of C-peptide response to the MMTT [Time points: weeks 13±1, 26±2 and 52±2].
3. Average (previous 3 days) insulin requirement (IU/kg/day) [Time points: baseline, weeks 13±1, 26±2 and 52±2].  
For the patients reporting “off insulin” response in the CRF the daily insulin requirement value will be conventionally set to zero in the statistical analysis.
4. HbA1c levels [Time points: baseline, weeks 13±1, 26±2 and 52±2].
5. Number of severe hypoglycemic events occurring from randomization [Time points: weeks 13±1, 26±2 and 52±2].  
A severe hypoglycemic event is defined as an event with one of the following symptoms: “Memory loss, confusion, uncontrollable behavior, irrational behavior, unusual difficulty in awakening, suspected seizure, seizure, loss of consciousness, or visual symptoms”, in which the patient was unable to treat him/herself and which was associated with either a blood glucose level < 54 mg/dL or prompt recovery after oral carbohydrate, i.v. glucose, or glucagon administration.
6. Basal (2 basal samples in the range between -20 to 0 min) to 180 min time course of C-peptide and glucose derived from the MMTT [Time points: baseline, weeks 13±1, 26±2 and 52±2].
7. Proportion of patients maintaining a residual β-cell function [Time points: baseline, weeks 13±1, 26±2 and 52±2].  
Maintenance of a residual β-cell function is defined as at least one MMTT C-peptide value > 0.2 nmol/L.
8. Proportion of patients with HbA1c < 7% and absence of episodes of severe hypoglycemia from the previous visit [Time points: weeks 13±1, 26±2 and 52±2].
9. C-peptide AUC (15-120 minutes) above fasting value [Time points: baseline, weeks 13±1, 26±2 and 52±2].

Document: MEX0114\_SAP\_v4\_4 Final Methods.docx  
 Author: [name]

Version Number:  
 Version Date:

Final Version 4.4  
 [17SEP2019]

Template No: CS\_TP\_BS016 – Revision 4  
 Effective Date: 01Apr2016

Reference: CS\_WI\_BS005

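### Appendix 14.4.2 allows short-acting insulin closer to the MMTT (2 h) than rapid-acting insulin (6 h); the two limits are apparently transposed

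*Protocol*

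**What the plan says.** Protocol Appendix 14.4.2 sets the conditions for every MMTT, at baseline and at weeks 13, 26 and 52. The test follows an overnight fast, starts before 10 a.m. and is done according to a cited published method. Three sentences deal with insulin and glucose:

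- Long-acting: "patients will withhold long-acting insulin on the morning of the test".
- The other two classes: "Rapid-acting and short-acting insulin will be allowed up to 6hrs and 2 hrs, respectively, before the test".
- Glucose check: "Test will be re-scheduled if the patient has a capillary glucose value of >200mg/dL or <70mg/dL".

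The middle sentence is the only statement of these limits. Nothing else in the protocol repeats or corrects it, and the SAP has no insulin rule for the test.

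Both classes are in scope. The only insulin regimens that Protocol 6.5.2 rules out are "Twice daily pre-mixed insulin or insulin pump".

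The test feeds three uses of C-peptide:

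- the primary variable, the 2-hour AUC at week 13 (SAP 16.1.1);
- eligibility, "Residual β -cell function as per peak stimulated (MMTT) C-peptide level" above 0.2 nmol/L (Protocol 5.1);
- the SAP's residual-function endpoint, which "is defined as at least one MMTT C-peptide value > 0.2 nmol/L" (SAP 16.2.1).

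**The concern.** The sentence before this one holds back the longest-acting class, so one expects the required interval to lengthen with duration of action. For the remaining two classes it does the opposite. Short-acting insulin, which acts longer, may be taken until 2 h before the meal. Rapid-acting insulin, which wears off sooner, must stop at 6 h.

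Insulin still acting during the test lowers glucose and therefore the stimulus for C-peptide. What is at stake is the standardization of the primary measure. Sites that follow the text and sites that assume a slip will prepare patients differently. Some readings could be lowered, and a patient very close to 0.2 nmol/L could be put on the wrong side of that threshold.

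**Working it through.** **Inputs from the documents.** Limits as written: rapid-acting 6 h, short-acting 2 h. AUC window: 0-120 min. Start before 10 a.m., fasted. Plan power: 85% with 72 patients, 2:1, one-sided 0.05, a 50% difference and 24% drop-out (Protocol 9.1).

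**Assumed, because the documents do not give them.** Durations of action: rapid-acting 3-5 h, short-acting 5-8 h. Action is treated as on or off, which overstates the weight of its last hours. The share of tests affected and the size of the effect are also assumed.

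**Step 1: action left in the AUC window after a dose taken exactly at the limit.** Minutes = min(120, max(0, 60 × (duration − interval))), both in hours.

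| Class and limit | Minutes of the 120 |
|---|---|
| Short-acting, 2 h (as written) | 120 for 5-8 h |
| Rapid-acting, 6 h (as written) | 0 for 3-5 h |
| Short-acting, 6 h | 0 for 5-6 h; 60 for 7 h; 120 for 8 h |
| Rapid-acting, 2 h | 60 for 3 h; 120 for 4-5 h |

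As written, a compliant short-acting dose overlaps the whole window and a compliant rapid-acting dose overlaps none of it. A rapid-acting dose at 4 h, with at most 60 min of action left, would be a breach. The reversal holds across the whole assumed range.

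**Step 2: would a plain exchange of the numbers reduce overlap?** Let s be the share of pre-test doses that are short-acting, S6 the short-acting overlap at 6 h and R2 the rapid-acting overlap at 2 h. Break-even is 120s = s × S6 + (1 − s) × R2, so s = R2 / (120 − S6 + R2).

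- S6 = 0: 60/180 = 0.33 with R2 = 60; 120/240 = 0.50 with R2 = 120.
- S6 = 60: 60/120 = 0.50 with R2 = 60; 120/180 = 0.67 with R2 = 120.
- S6 = 120: 1.00, so no gain is possible.

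The gain from moving rapid-acting insulin to 2 h therefore depends on a mix of doses that the documents do not give. Lengthening the short-acting limit to 6 h, with rapid-acting left alone, never increases overlap, though at 8 h it gains nothing.

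**Step 3: which doses are affected.** For a test at 10 a.m., the two limits fall at 4 a.m. and 8 a.m. Only a dose between those times, in a fasting patient, is treated differently by class.

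**Step 4: effect on power (normal approximation).** The plan gives no SD, so it is backed out of the stated 85%.

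- Evaluable: 72 × 0.76 = 54.7, or 36.5 against 18.2.
- Difference/SD = (1.645 + 1.036) × √(1/36.5 + 1/18.2) = 0.769.
- Taking the 50% difference as ln(1.5) = 0.405 (plain log in place of log(x+1)), SD = 0.405/0.769 = 0.527 and variance = 0.278.
- If a share p of tests in each arm has its AUC lowered by a fraction e, the added variance is p(1 − p)[ln(1 − e)]².
- Power = Φ(2.681/√(1 + added/0.278) − 1.645).

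| p | e | Added variance | Increase | Power |
|---|---|---|---|---|
| 0.02 | 0.10 | 0.0002 | 0.1% | 85.0% |
| 0.05 | 0.20 | 0.0024 | 0.9% | 84.7% |
| 0.10 | 0.30 | 0.0115 | 4.1% | 83.7% |

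**Step 5: effect at 0.2 nmol/L.** A lowered reading falls to 0.2 or below only if the true peak is at most 0.2/(1 − e): 0.222, 0.250 and 0.286 nmol/L for e = 0.10, 0.20 and 0.30. Only patients just above the threshold are exposed.

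**The case against.** The documents state no duration of action for either class, and the cited method is out of reach. Strictly, they support a query to the sponsor and do not prove a slip. That stands, and it is why the transposition is called apparent.

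Exposure is also narrow. Patients are fasted, the early-morning dosing interval is short, and the investigator reviews glucose in the two weeks before each visit to "confirm/adjust insulin intake to be applied for at least 3 days before the visit". Tests with glucose outside 70-200 mg/dL are re-scheduled. All of this stands as a limit on size. The glucose check, however, tests glucose and not insulin action: a patient at 120 mg/dL with short-acting insulin still working passes.

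The strongest counter-argument is that a late dose may be allowed on purpose, so that the patient passes the glucose check. That purpose would favour the faster class at 2 h, which is again the reverse of the text. No reading makes the written order sensible.

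A reader might go further and infer that 2 h is simply too short for a washout. The appendix states no washout aim for these two classes and sets no standard against which 2 h could fail. What can be shown is the order of the two limits. A reader might also infer that 6 h should be imposed on both classes for good. Nothing in the documents supports that rule, and it may depart from the method the protocol adopts.

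**Conclusion.** The point holds as a minor error of wording. The two limits are in the wrong order relative to duration of action, and they are apparently transposed. That rests on the assumed durations, though the order holds throughout their range, and on no sight of the cited method.

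The likely consequence is a small, non-differential increase in the variability of the C-peptide AUC, possibly nil. Even in the largest illustrated case (10% of tests affected, AUC 30% lower) power goes from 85% to 83.7%. These shares and effects are assumptions, since neither document gives the mix of insulin classes or the frequency of doses 2-6 h before a test.

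A reader might infer a biased treatment comparison. The documents do not support that. The rule is the same in both blinded arms, Protocol 9.2 balances treatment within centres, and any effect on screening falls before randomization.

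**What to change.** - **Check and correct the sentence.** Compare it with the cited MMTT method and put the order right, so that short-acting insulin has the longer limit: not within 6 h of the test. Rapid-acting insulin should have the interval the cited method gives, apparently 2 h. Keep the present 6 h for rapid-acting insulin until that is confirmed, because 2 h could leave it active for 60-120 min of the window (step 1).
- **Tell all sites**, by amendment or clarification letter.
- **Record the class and clock time of the last insulin dose at each MMTT**, if not already captured. Exposure can then be measured instead of assumed.

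No planned analysis changes. Naming a breach among the major deviations in SAP 6.5 is optional and would affect tabulation only: "All the protocol deviations will be discussed case by case by the clinical team" already, and all efficacy analyses use the ITT set (SAP 16).

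The cost is one sentence and at most two CRF fields, plus some tests re-scheduled for glucose above 200 mg/dL. Re-scheduling uses up part of the ±1 week window at week 13, where a late or missing primary AUC counts as a major deviation, and part of the pre-randomization window at baseline.
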